8.11.5.2 Causal relationship and seriousness

Each AE shall be assessed by the Investigator for causal relationship with the study product and its use (the injection procedure) and for seriousness (Yes or No) of the event.

A two-point scale (Yes or No response) shall be used for the causality assessments. The Investigators shall be asked to indicate a response to each of the following questions in the eCRF:

- ☐ “Do you consider that there is a reasonable possibility that the event may have been caused by the study product?”, and

□

“Do you consider that there is a reasonable possibility that the event may have been caused by the study product injection procedure?”

If any of these questions is answered Yes, the AE is considered related.

Each AE will also be assessed for causal relationship and seriousness by the Sponsor, in order to fulfill regulatory requirements.

In addition, each SAE will be classified by both the Investigator and Sponsor separately, according to four different levels of causality:

1. **Not related** - Relationship to the device, comparator or procedures can be excluded when:

- the event has no temporal relationship with the use of the investigational device, or the procedures related to investigational device;
- the serious adverse event does not follow a known response pattern to the medical device (if the response pattern is previously known) and is biologically implausible;
- the discontinuation of medical device application or the reduction of the level of activation/ exposure - when clinically feasible - and reintroduction of its use (or increase of the level of activation/exposure), do not impact on the serious adverse event;
- the event involves a body-site or an organ that cannot be affected by the device or procedure;
- the serious adverse event can be attributed to another cause (e.g. an underlying or concurrent illness/ clinical condition, an effect of another device, drug, treatment or other risk factors);
- the event does not depend on a false result given by the investigational device used for diagnosis, when applicable;

In order to establish the non-relatedness, not all the criteria listed above might be met at the same time, depending on the type of device/procedures and the serious adverse event.

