10.5 Safety analysis

All AEs will be coded according to MedDRA and summarized by system organ class (SOC), preferred term (PT) and treatment (no treatment, 1st treatment including touch-up if applicable, and 2nd treatment).

A summary of all AEs will be provided, which will include:

- number of subjects with at least one AE and number of events (in total as well as serious AEs)
- number of subjects with at least one related AE and number of events (in total as well as serious AEs)
- number of subjects with at least one unrelated AE and number of events (in total as well as serious AEs)
- number of subjects who did not have an AE

The number of subjects with AEs related to study product or injection procedure as well as the number of events will be summarized by SOC, PT and maximum severity. In addition, for related AEs the number of days to onset and the duration of event will be summarized by SOC and PT using mean, SD, min, max and median. Action taken for related AEs will also be summarized. Serious AEs, and AEs with onset >21 days after most recent treatment will be listed.

Non-related AEs will be summarized by SOC, PT and intensity.

To evaluate consistency of AEs across different subgroups, AEs will also be summarized by subgroups defined as described below.

Safety analysis will be descriptive only.

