10.6.2 Safety

The consistency of AE data across different subgroups will also be evaluated. The following subgroup factors will be used:

- Injection tool (needle, cannula, and combination)
- Study site
- FST group (I-III, and IV-VI)
- Injection volume (\leq median total injection volume vs $>$ median total injection volume)
- Gender
- Age (\leq median age vs $>$ median age).

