2.1 General Methods

Any change made to the finalized SAP before database lock will result in an SAP amendment. Otherwise, changes will be documented in the Clinical Study Report (CSR). However, if additional supportive or exploratory analyses are requested after SAP approval, this will not require amendment of the SAP, but these additional analyses will be described in the CSR.

Some of the analyses detailed here may be more explicit or in some respects different from those stated in the protocol. In case of differences, this SAP supersedes the statistical sections in the protocol.

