2.2.3 Safety Population

The Safety population includes all subjects who were treated with GP0109 or randomized to the no treatment control group, and will be analyzed according to the as-treated principle. All safety data will be summarized descriptively based on the Safety population.

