2.5.2 Adverse Events (AEs)

All AEs will be summarized relative to treatment session timing using the following categories:

- No Treatment at Baseline: For subjects who receive no treatment at baseline, include AEs before any optional GP0109 treatment at Month 12.
- Initial Treatment with GP0109: Pool AEs for the following (whether optional touch-up treatment received or not):
 - For subjects treated with GP0109 at baseline:
 - include AEs before optional GP0109 re-treatment at Month 12,
 - include AEs through end of study if no re-treatment at Month 12.
 - For subjects who receive no treatment at baseline, include AEs after initial GP0109 treatment at Month 12.
- Re-treatment with GP0109: For subjects treated with GP0109 at baseline, include AEs after optional GP0109 re-treatment at Month 12.

All AEs will be coded according to MedDRA and summarized by System Organ Class (SOC), Preferred Term (PT), and treatment session timing as described above. The number of subjects with at least one event, associated percentage, and number of events will be provided.

For subject counts, a subject will only be counted once per SOC and once per PT in cases where multiple events are reported for a subject within SOC or PT. For event counts, subjects with multiple events in a category will be counted for each event.

The number of subjects with AEs related to study product or study product injection procedure and unrelated AEs, as well as the number of events, will be presented by SOC, PT, and maximum intensity. Action taken for related AEs will also be summarized by SOC and PT using number of events. AEs related to study product or injection procedure with late onset (> 21 days after most recent treatment session) will be listed.

Serious AEs and AEs of special interest (AESIs) will be listed. See Section 8.2.1 of the protocol for a list of visual disturbances considered to be AESIs.

For AEs related to study product or study product injection procedure, the number of days to onset and the duration of event will be summarized by SOC and PT using mean, standard deviation, median, minimum, and maximum. Days to onset of an AE will be derived as the start date minus the date of most recent treatment session. Duration of an AE will be derived as the stop date minus the start date + 1. Missing stop date will not be imputed, and therefore no duration will be calculated in these cases.

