In addition, a summary of all AEs will be provided, which will include (but is not limited to):

- number of subjects with at least one AE and number of events (in total as well as serious AEs),
- number of subjects with at least one related AE and number of events (in total as well as serious AEs),
- number of subjects with at least one AESI and number of events,
- number of subjects with at least one unrelated AE and number of events (in total as well as serious AEs),
- number of subjects who did not have an AE.

To evaluate consistency of AEs across different subgroups, related AEs by SOC, PT, and maximum intensity will also be summarized by subgroups, specifically injection tool (needle, cannula, and combination), study site, FST (I-III and IV-VI), race, ethnicity, gender, age group (\leq median age and $>$ median age), and total injection volume group (\leq median total injection volume and $>$ median total injection volume). Pooling of subgroup categories may be needed based on observed data.

CCI

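### The SAP narrows the subgroup AE tables from all AEs to related AEs without visibly declaring it, so those tables carry almost no untreated background rate

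*SAP*

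**What the plan says.** Protocol section 10.5 states: "To evaluate consistency of AEs across different subgroups, AEs will also be summarized by subgroups defined as described below". Section 10.6.2 repeats the intention, "The consistency of AE data across different subgroups will also be evaluated", and lists six factors: injection tool, site, Fitzpatrick group, injection volume, gender and age. Neither sentence mentions causality. Elsewhere in 10.5 the protocol does limit items to related events where it means to, for example time to onset, duration and action taken.

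SAP section 2.5.2 keeps the purpose (consistency of AEs across subgroups) and adds race and ethnicity to the factors, but narrows the events: "related AEs by SOC, PT, and maximum intensity will also be summarized by subgroups". No other visible SAP text plans all AEs, or unrelated AEs, by subgroup.

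Three other provisions bear on the point:

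- **Relatedness** (Protocol 8.11.5.2). The investigator answers one question on causation by the product and one on causation by its injection procedure. "If any of these questions is answered Yes, the AE is considered related".
- **Untreated category** (SAP 2.5.2). "For subjects who receive no treatment at baseline, include AEs before any optional GP0109 treatment at Month 12". Controls belong to the Safety population, which "includes all subjects who were treated with GP0109 or randomized to the no treatment control group".
- **Precedence** (SAP 2.1). "In case of differences, this SAP supersedes the statistical sections in the protocol". SAP 2.8, which is partly redacted, reports no substantial change apart from the additions in 2.4.4.

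**The concern.** A subgroup table of related AEs shows how often investigators attributed events to treatment in each subgroup. It does not show how often events of the same kind arose in untreated subjects of that subgroup. A difference by age or skin type may be a treatment effect or a background difference, and a related-only table gives no means of comparing the two.

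Two features of this trial add to the problem. First, causality is judged unblinded: the Treating Investigator knows the assignment and safety assessments are made by non-blinded staff (Protocol 4.4.2). Each site is assigned one injection tool in advance (SAP 1.1.2), so any difference between sites in attribution habits is mixed with the tool comparison. Second, some AEs are to be expected without treatment. A Snellen worsening of one line or more is reportable as an AE (Protocol 8.8.1), and visual function is tested in both arms at the common follow-up visits. Such events are also AESIs whatever their cause (Protocol 8.11.3). If judged unrelated, they are absent from every subgroup table.

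At stake is the subgroup safety description that the protocol promised, including that for Fitzpatrick IV-VI, for which the protocol sets recruitment minimums. No primary result or stopping rule depends on it.

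**Working it through.** **1. The plan's own safety figure.** SAP 2.7.5 gives about 80% probability of seeing at least one AE of 1% incidence among 168 treated subjects. 1 − 0.99^168 = 0.815, so the figure is reproduced. It is the only safety sample-size figure and the point does not depend on it.

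**2. Text comparison.**

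| Element | Protocol 10.5 / 10.6.2 | SAP 2.5.2 |
|---|---|---|
| Stated purpose | consistency of AEs across subgroups | the same |
| Events tabulated | AEs | related AEs |
| Factors | six | eight (race and ethnicity added) |
| Change visibly declared in SAP 2.8 | – | no |

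The SAP was written to protocol version 3.0. The visible log of changes from version 3.0 to 4.0 lists nothing for 10.5 or 10.6.2. A change of version is therefore an unlikely explanation, although part of that log is redacted.

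**3. Why the untreated column is near zero.** A related AE needs a Yes to causation by the product or its injection procedure. The untreated category contains only time before any GP0109 exposure. A subject with neither product nor injection can have a related AE only through a mistaken or unusual causality answer. The expected count is therefore about 0 in every subgroup, whatever the true AE rate.

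**4. What the protocol's version would show.** Inputs: 224 subjects, 3:1 allocation, three tools, at least 45 subjects in Fitzpatrick IV-VI, about 15 subjects per site. Expected control denominators at randomization, before dropout:

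- All controls: 224/4 = 56
- Fitzpatrick IV-VI at the minimum: 45/4 = 11.25, about 11
- Fitzpatrick I-III: (224 − 45)/4 = 44.75, about 45
- Per injection tool: 56/3 = 18.7, about 19
- Per half of the median age split: 56/2 = 28
- Per site: 15/4 = 3.75, about 4

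The documents give no background AE rate. With assumed rates of 10%, 20% and 30%, rounded to whole subjects, the exact (Clopper-Pearson) 95% intervals are:

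| Controls | 10% | 20% | 30% |
|---|---|---|---|
| Fitzpatrick IV-VI, n = 11 | 1/11: 0.2–41% | 2/11: 2–52% | 3/11: 6–61% |
| One tool, n = 19 | 2/19: 1–33% | 4/19: 6–46% | 6/19: 13–57% |

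A background rate would thus be available but imprecise.

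**5. Purely hypothetical illustration of attribution.** Suppose 40% of treated subjects have an event at every tool, and that sites using one tool call 95% of these related while sites using another call 75%. The related-AE table would show 0.40 × 0.95 = 38% against 0.40 × 0.75 = 30%, and an all-AE table 40% against 40%. None of these rates comes from the documents. The example shows the mechanism, not its likely size.

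**The case against.** The strongest reply is that little is lost. "All AEs will be summarized relative to treatment session timing using the following categories", and these include an untreated category, so the trial as a whole has a background rate. Unrelated AEs are also presented overall, and AESIs are listed and counted. This stands: what is missing is only the breakdown by subgroup.

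A reader might infer that the 56 controls contribute nothing to any subgroup AE table. The documents do not support that. Under SAP 2.5.2, a control who takes GP0109 at Month 12 has later AEs counted under *Initial Treatment with GP0109*, so related events from such subjects do appear. Only the pre-treatment column is near zero.

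A reader might also infer that only all-cause AEs can separate attribution from incidence. That is too strong. The sponsor also assesses causality for every AE, all sites answer the same two questions (Protocol 8.11.5.2), and subject diaries ask directly about pre-identified symptoms for 28 days after each session (SAP 1.4). Whether diary symptoms are broken down by subgroup is not visible.

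Several further points stand. Related events across treated subgroups are a sensible display for tool and volume. Untreated subjects have no injection volume, so that factor has no natural untreated column. Safety analysis is descriptive and the untreated denominators are small. The SAP categories are not a clean randomized contrast either: initial treatment pools both arms and can run to Month 24, while untreated time ends at Month 12. Finally, all data are listed, and SAP 2.1 allows supportive tables without an amendment.

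These points narrow the concern but do not remove it. The protocol promised small descriptive tables of AEs by subgroup, and tables specified in advance are worth more than tables requested once results are known.

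**Conclusion.** The concern holds in a limited form. SAP 2.5.2 replaces the protocol's subgroup summary of AEs with one of related AEs, prevails by its own rule, and does not visibly declare the change. In the subgroup tables only, this leaves the *No Treatment at Baseline* column near zero by construction and omits events judged unrelated, AESIs among them. It does not deprive the trial of a background AE rate.

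The size is modest: an absent breakdown over denominators of about 11 controls in Fitzpatrick IV-VI, about 19 per tool and about 4 per site. The conclusion rests on the visible text, since parts of SAP 2.8 and the amendment log are redacted, and on causality being answered as Protocol 8.11.5.2 defines it. No claim is made about how much attribution actually differs between sites.

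**What to change.** In SAP 2.5.2:

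1. Add subgroup tables for all AEs (subjects, percentages and events) by treatment category, for the factors already listed.
2. Limit the treated-versus-untreated display to the randomized arms and to events up to Month 12 before any optional treatment, so that follow-up is comparable.
3. For injection volume, show controls as one pooled column. Tool and site can use their own controls, because each site has one assigned tool.
4. Keep the related-AE subgroup tables as a second set.

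If the sponsor prefers the restriction, SAP 2.8 should at least declare and justify it.

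The cost is SAP wording and one more set of descriptive tables. No new data are needed: AEs are collected from randomization in both arms and recorded regardless of cause (Protocol 8.2 and 8.11.6). The drawback is that some untreated cells will be very small, above all by site, and the tables should say so.

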2.5.4 Other Safety Analyses

Assessments of jawline mobility, intra-oral exam, pronunciation, jawline sensation, facial nerve function, palpation, visual function (Snellen visual acuity test, extraocular muscular function test, and confrontation visual field test), and device deficiencies will be summarized descriptively as appropriate.

For subjects who received no treatment at baseline, other safety assessments will be summarized in the tables under one column for “No Treatment at Baseline”. Based on visit timing, results at or prior to Month 12 will reflect assessments after no treatment at baseline. Results after Month 12 will reflect assessments after the optional GP0109 treatment at Month 12 (since subjects declining such treatment will end the study). For subjects treated with GP0109 at baseline (whether optional touch-up treatment received or not), other safety assessments will be summarized in the tables under one column for “GP0109”, where results $>$ Month 12 will use subjects re-treated or not at

Month 12 (since subjects will continue in the study if optional re-treatment at Month 12 is declined).

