8.5 Palpability

The Investigator will palpate the jawline for detection of any unexpected feel such as nonuniform density or unexpected lumpiness at baseline and all physical follow-up visits thereafter. The study products are generally palpable (i.e. can be felt under the skin) and have uniform density. Any unexpected feel upon palpation will be assessed as “Abnormal” and should be reported as an AE by the Investigator, and should include a description of the localization, feel, and approximate size.

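### The Month 15–24 tables of objective safety tests merge re-treated and not-re-treated GP0109 subjects, so they cannot show the proportion abnormal in either group

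*SAP*

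**What the plan says.** SAP Section 2.5.4 covers "Assessments of jawline mobility, intra-oral exam, pronunciation, jawline sensation, facial nerve function, palpation, visual function" and device deficiencies, all summarised descriptively. Two columns run through the whole study.

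- **'No Treatment at Baseline'.** Up to Month 12 this shows untreated controls. Later, "Results after Month 12 will reflect assessments after the optional GP0109 treatment at Month 12", because controls who decline leave the study.
- **'GP0109'.** This holds everyone treated at baseline, with or without touch-up, "where results $>$ Month 12 will use subjects re-treated or not at" Month 12. The reason given is "since subjects will continue in the study if optional re-treatment at Month 12 is declined".

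SAP Section 2.5.2 treats adverse events (AEs) differently and gives them their own category: "Re-treatment with GP0109: For subjects treated with GP0109 at baseline, include AEs after optional GP0109 re-treatment at Month 12". Protocol Section 10.5 likewise lists the second treatment separately for AEs, and SAP Section 2.5.1 summarises injection volume by treatment session. No table of the objective tests by re-treatment status is described in either document.

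**The concern.** At Month 12 the baseline-treated arm divides into subjects who receive a second treatment and subjects who do not. From then on their exposure differs, but the by-visit tables of objective tests do not follow the division. The reason the SAP gives is that decliners stay in follow-up. That explains why both groups exist after Month 12, not why they should share a column.

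The second year is this trial's only source on repeat treatment and on the long-term course after a single treatment. If abnormal findings are more frequent after re-treatment, the pooled proportion is too low for re-treated subjects and too high for the others. A reader of the tables could not tell how far off it is in either direction.

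The column also changes population between visits. Visits 7b and 7c take place only if treatment was given at Month 12 (footnote 4 of the schedule of events), so 'GP0109' there contains re-treated subjects only. From Visit 8 it is a mixture. A fall in abnormal findings from Visit 7c to Visit 8 could come entirely from who is being counted.

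**Working it through.** **1. Exposure at Visit 8.** A study month is 28 days, so Month 15 is nominally day 15 × 28 = 420 and Month 12 is day 336. A re-treated subject is 420 − 336 = 84 days from the last injection. A subject not re-treated is 420 days from it, or 420 − 28 = 392 days after a 1-month touch-up. Both are counted in one proportion.

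**2. Which abnormal findings also reach the split AE tables.** This decides where the pooling does harm.

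| Test | Protocol section | Route to an AE |
|---|---|---|
| Palpation | 8.5 | Any unexpected feel is rated abnormal "and should be reported as an AE by the Investigator, and should include a description of the localization" |
| Visual acuity, eye movement, visual field | 8.8.1–8.8.3, 8.11.3 | Worsening is reported as an AE and is an AE of special interest |
| Facial nerve | 8.6 | Only if abnormal and clinically significant |
| Sensation | 8.4 | Assessed as a potential AE |
| Jaw mobility, intra-oral exam, pronunciation | 8.3 | Abnormal findings evaluated as potential AEs |

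For the first two rows, re-treatment findings will be visible in the AE tables. For the rest, an abnormal result that the investigator does not call an AE appears in summary form only in the pooled table.

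**3. What the AE tables cannot replace.** They group events by treatment session, not by visit, so they give no proportion abnormal at Months 15, 18, 21 or 24. Their initial-treatment category combines baseline-treated subjects with controls first treated at Month 12, so it does not isolate long-term single treatment either.

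**4. Dilution (assumed values).** Let f be the re-treated share, p2 the abnormal rate if re-treated and p1 the rate if not. The pooled column shows f·p2 + (1 − f)·p1. Neither f nor the rates are in the documents. Take p2 = 10% and p1 = 2%:

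- f = 25%: 0.25 × 10 + 0.75 × 2 = 4.0%
- f = 50%: 0.50 × 10 + 0.50 × 2 = 6.0%
- f = 75%: 0.75 × 10 + 0.25 × 2 = 8.0%

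On the same values with f = 50%, the 'GP0109' column would go from 10% at Visit 7c to 6% at Visit 8 with no change in either group's rate.

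**5. Cost in precision.** The plan's only safety-precision figure is about an 80% chance of seeing at least one event of 1% incidence in 168 treated subjects (SAP 2.7.5). It reproduces: 1 − 0.99^168 = 0.815. For a re-treated column, with n = f × 168 and no loss to follow-up:

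| f | n | P(at least one event) = 1 − 0.99^n | 95% upper bound with zero events = 1 − 0.05^(1/n) |
|---|---|---|---|
| 25% | 42 | 34% | 6.9% |
| 50% | 84 | 57% | 3.5% |
| 75% | 126 | 72% | 2.3% |
| pooled | 168 | 82% | 1.8% |

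With 10% lost (151 subjects remaining), the three probabilities fall to 32%, 53% and 68%.

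**The case against.** A reader might infer that the trial cannot show what a second treatment does to vision, palpation, sensation, nerve or jaw function. The documents do not support that. AEs have a separate re-treatment category. Abnormal palpation and visual worsening must be reported as AEs, and AEs of special interest are counted and listed. Related AEs are given days to onset from the most recent treatment. Visits 7b and 7c are unmixed, so results 14 days and 1 month after the second injection are already isolated. All case report form data are listed by subject, so a split can be made at any time.

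It can also be said that Section 2.5.4 states openly what each column contains, that protocol Section 10.5 on treatment session governs AEs only, and that visit-based results may reasonably be shown by original arm. Re-treatment is not randomised: it depends on loss of improvement and on choice. A split would therefore not identify a causal effect, and it reduces denominators.

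Most of this stands, and it limits the point to the Month 15–24 summary tables and mainly to the tests whose AE reporting is discretionary. It does not remove the gap. Listings give no rates. Lack of randomisation did not stop the SAP from splitting AEs. The pooled column's 82% is the chance of seeing an event in anyone in the mixture; the chance of an event among re-treated subjects depends on how many there are, however the table is laid out.

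**Conclusion.** The point holds for the planned by-visit tables at Months 15–24 (Visits 8–11). They cannot show the proportion abnormal after re-treatment, or in the long term after a single treatment, although the AE tables separate re-treatment. It matters most for sensation, jaw mobility, pronunciation, intra-oral findings and facial nerve abnormalities judged not clinically significant. It matters least for palpation and vision.

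The size cannot be fixed from the documents. Under the assumed 10% and 2%, the pooled figure is 40% to 80% of the re-treated rate (4/10 to 8/10) and two to four times the not-re-treated rate (4/2 to 8/2) as the re-treated share runs from 25% to 75%. If the two groups have the same rate, nothing is diluted.

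This is a reporting gap, not a loss of data. It does not affect the primary endpoint or the randomised safety comparison up to Month 12.

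**What to change.** Amend SAP Section 2.5.4 and the table formats before database lock:

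- **Through the pre-treatment Month 12 assessment:** keep the two randomised columns.
- **Visits 7b and 7c:** keep two columns, labelled as re-treated at Month 12 and first treated at Month 12. A not-re-treated column would be empty here.
- **Visits 8–11:** use three columns: GP0109 at baseline, not re-treated; GP0109 at baseline, re-treated at Month 12; first GP0109 treatment at Month 12. A pooled GP0109 total can be added.
- **Footnote:** state that re-treatment was not randomised and that the comparison is descriptive.

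The cost is SAP wording and table formats only, since Month 12 treatment is already recorded. Denominators are smaller, as shown in the working, and the optional total column preserves the pooled figure.
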